Research Design. The proposed intervention will recruit 15 children with PMS and 15 children with iASD (2-12 years old). Treatment will follow a randomized, placebo-controlled, crossover format with 12 weeks in each treatment phase (rhGH and placebo). This duration was selected based on evidence with IGF-1 in PMS suggesting our clinical outcomes will be sensitive to change within this time frame (Kolevzon et al., 2014). The primary electrophysiological outcomes will be VEP gamma band activity as our preliminary data with PMS in IGF1 suggests it is sensitive to drug effects (Fig. 5). The primary clinical outcome will be the SAND because: a) our preliminary studies suggest improvement on this measure following IGF-1 (Fig. 6), b) it accurately reflects a sensory phenotype characteristic of PMS and is relevant to a substantial subset of iASD, c) it is associated with electrophysiological measures, and d) it has been validated in ASD and ID.

Inclusion criteria: All participants with PMS will have pathogenic *SHANK3* deletions or sequence variants confirmed in clinical genetics laboratories approved by the Clinical Laboratory Improvement Amendments (CLIA). Genotyping will also be used to confirm the absence of known pathogenic copy number variants in the iASD group. Participants with iASD will meet gold standard diagnostic criteria for ASD, confirmed by the Autism Diagnostic Observation Schedule – 2nd Edition (ADOS-2; Lord et al., 2012) and the Autism Diagnostic Interview-Revised (ADI-R; Lord et al., 1994). All iASD subjects will have a reduced neural response defined by $P_{60}-N_{75}$ amplitudes within one standard deviation of the PMS mean. Subjects will be on stable medication and psychosocial treatment regimens for at least three months prior to enrollment.

Exclusion criteria: 1) closed epiphyses; 2) active or suspected neoplasia; 3) intracranial hypertension; 4) hepatic insufficiency; 5) renal insufficiency; 6) cardiomegaly/valvulopathy; 7) allergy to growth hormone or any component of the formulation; 8) comorbid conditions which prevent participation; 8) visual problems which preclude use of VEP.

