Data Analysis. Following the procedures of a 2x2 cross-over design, each subject is randomized to one of two treatment sequences. First we will use graphical and numerical statistics to characterize treatment-, period- and cross-over effects (Jones & Kenward, 1989). Under the assumption of no cross-over effects and data following an approximate normal distribution, we will fit generalized linear mixed models (GLMMs) to the data examining the effects of group (PMS, iASD), condition (placebo, drug), time (baseline, week-12). Interactions on clinical and VEP measures will be checked for differential treatment effects, including subject level random

intercepts, to control for within subject correlations. Next, we will add baseline VEP gamma band activity, along with its interactions, to the models for clinical outcomes. In particular, a VEP by group by time interaction would suggest that the electrophysiological marker is predictive of differential treatment response. We will repeat these analyses with secondary electrophysiological markers and any derived composites. To examine whether electrophysiological markers track changes in clinical profiles, we will fit an additional GLMM with VEP values included as a time-varying rather than baseline covariate. If treatment effects become less significant it will suggest that rhGH is acting on clinical outcomes through the biomarker. Finally, we will directly correlate week-12 change scores for EEG and clinical measures. In case of major cross-over effects, we will base our primary analysis on phase 1 data only as a parallel group study. All tests will use a two-sided α of .05.

Power Analysis: Power is calculated for drug group differences in baseline to week 12 change scores in VEP gamma power since we are primarily interested in an overall treatment effect rather than a differential effect by group. These correspond to paired t-tests, taking advantage of the crossover design. With α at .05, we have 80% power to detect moderate to large effects ($d=.77$ within each group, $d=.53$ across groups), a reasonable expectation based on the potentially disease modifying effects of IGF-1 and our pilot study, which found a large effect ($d=1.05$) of IGF-1 in PMS on a different primary outcome (ABC-SW).

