Potential pitfalls and alternative strategies. We expect loss of some electrophysiological data due to the severely affected nature of the population; however, this study is well powered and our proposed sample size can accommodate attrition and still detect meaningful differences across a range of responses. We have been successful in recording VEP in more than 70% of patients with PMS seen in our center. We will implement a sensory desensitization and behavioral training protocol and have extensive experience collecting these data from children with ASD, PMS, and severe ID. Moreover, for the VEP, short-duration stimulus conditions are being utilized. In addition, crossover trial designs carry risks of contamination effects, so we have provided a four-week washout period to minimize this risk. We have not observed significant carryover effects in our preliminary data. We believe this design is important because all patients will be afforded the opportunity to receive active medication. Second, the burden of frequent monitoring visits and subcutaneous injections risks increase the risk of subject withdrawal. Given the rigid control of the study procedures, relatively simple measurement techniques, and based on our experience to date, we do not foresee any major loss of data due to drop-outs or missing values. Still, in case of drop-outs we will use the intent to treat principle so all randomized patients will be included in the data analysis. Third, because of concerns about recruitment feasibility, we have established an excellent working relationship with the national PMS Foundation. Fourth, because we are only enrolling patients with iASD with PMS-like VEP amplitudes, we will not be able to test the *specificity* of target engagement and successful treatment response. Finally, if VEPs cannot be established as a biomarker for stratification or efficacy, we still have a wealth of other electrophysiological and clinical outcomes that will provide critical information.

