particularly uncomfortable for children with developmental disabilities and will be kept to a minimum to reduce risks. The procedures for minimizing risk include assisting parents in keeping their child still, the use of a special lounge chair to help the child relax during the procedure, the use of numbing cream if needed to reduce pain, and the use of professionals in the Mount Sinai Clinical Research Center who are trained and certified in blood drawing procedures in children with developmental disabilities.

The risks in participating in the electrophysiology aims of this study are minimal. The physical contacts with the instruments are limited to the standard EEG electrodes placed on the scalp. Electrodes are disinfected between participants. It is possible that as a result of participating in electrophysiological testing, participants may experience fatigue or anxiety. We will attempt to minimize potential discomfort from testing/evaluation by providing frequent breaks during the visits. If the participant finds any discomfort during the EEG intolerable, he or she will be withdrawn from the study. If the participant feels uncomfortable, the participant or his/her parents can tell the investigators and ask to stop the EEG at any time. We will implement a sensory desensitization and behavioral training protocol in which participants will have the opportunity to practice mock EEG procedures over the course of visits. Participants will also receive a social story describing the components of their visit as needed. Visual schedules and positive reinforcement systems (e.g., token economies) will be used throughout testing.

A Data and Safety Monitoring Board (DSMB) has been convened and has primary responsibility for developing the oversight necessary to promptly identify and act upon any adverse events. The DSMB is made up of three physicians who will meet routinely every six months and immediately should a severe adverse event occur (please see attached DSMB Charter).

Adequacy of Protection Against Risks

Recruitment and Informed Consent:

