- Laboratory: any abnormality on any test with adverse event (AE, Common Terminology Criteria for Adverse Events, National Cancer Institute, scales) ≥ 3 or greater at any time in the study
- Any AE of any sort (clinical, laboratory) ≥ 4 will result in halting for the individual and also for the study as a whole.

To avoid bias, all analyses will include all subjects, including those withdrawn from the study, regardless of adherence to study protocol. Especially in an exploratory trial of a novel, unproven treatment, the safety of subjects is our primary *overriding* concern. If there is doubt concerning a subject's safety, the default mode will be withdrawal from treatment or active study participation, followed by close observation (safety follow up visits) and recommendation of standard treatment.

Return of a subject to active study participation will not be permitted, except if a transient clinical or laboratory abnormality unrelated to study treatment has occurred and subsequent permission of the Safety Monitoring Board to return the patient to active study has been provided.

If a subject is withdrawn from active study during screening or observation phases of the study, they will be returned to the referring physician and standard care will be recommended; in addition we will request the subject's participation in an end-of-study visit.

If a subject is withdrawn from active study during rhGH treatment, they will also be returned to the referring physician and standard care will be recommended; however, in this case, we will in addition request the subject's participation in clinical and laboratory safety assessments and follow up per protocol schedule.

Stopping Conditions for Study as a Whole

The study will be halted* if two patients experience stopping conditions. (Exceptions for this criterion: Patients who withdraw voluntarily for reasons not directly related to or intrinsic to the study, e.g. incidental considerations such as concerns about travel time to study visits, unexpected pregnancy in the family, etc. Clearly, patients who experience adverse effects during rhGH treatment would count towards this criterion for whole study stopping).

In addition, the study will be halted if one patient experiences a serious related adverse effect (grade \geq 4 AE).

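### The EEG-intolerance rule takes the child out of the whole study, so it truncates the SAND and other clinical outcomes that need no EEG, and it is not reconciled with the follow-up and stopping sections

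*Combined protocol and SAP*

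**What the plan says.** Protection of Human Subjects, Risks to the Subjects (electrophysiology paragraph): "If the participant finds any discomfort during the EEG intolerable, he or she will be withdrawn from the study". The sentence after it says that "the participant or his/her parents can tell the investigators and ask to stop the EEG at any time" and does not mention leaving the study.

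Potential pitfalls and alternative strategies: "We expect loss of some electrophysiological data due to the severely affected nature of the population". The same section foresees no major loss from drop-outs and invokes intent to treat, but names no missing-data method.

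Stopping Conditions for Individual Subjects: the list covers withdrawn consent, a judgement by the investigator or an oversight body, and graded adverse events. EEG intolerance is not named. The section then says: "To avoid bias, all analyses will include all subjects, including those withdrawn from the study, regardless of adherence to study protocol". After withdrawal during rhGH it requests "participation in clinical and laboratory safety assessments and follow up per protocol schedule". After withdrawal in screening or observation phases it requests one end-of-study visit. Withdrawal during placebo is not named. Return to active participation is barred, except after a transient abnormality unrelated to treatment and with the monitoring board's permission.

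Outcome measures: the SAND hyporeactivity subscale is the primary clinical outcome. EEG and clinical measures are both scheduled at baseline and weeks 4, 8 and 12 of each phase.

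**The concern.** One measurement procedure appears to decide whether a child stays in the trial. The SAND, the ABC Social Withdrawal subscale and the other clinical scales can be obtained without an EEG, yet a literal reading of the rule ends their collection when a recording is not tolerated. Keeping the child in the analysis set does not supply scores that were never collected.

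The design depends on each child contributing both phases. The power calculation is a paired one, and the sample of 30 carries no allowance for drop-out. A child withdrawn in phase 1 does not enter phase 2 and so gives no within-child comparison on any outcome.

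The two adjacent sentences also allow the same event to be handled in two ways, as a stopped recording or as a withdrawal. It is not stated whether such a withdrawal counts toward the rule that halts the study after two patients meet stopping conditions.

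**Working it through.** **Inputs.** N = 15 PMS + 15 iASD = 30 (Research Design). "All tests will use a two-sided α of .05" (Data Analysis). Paired t-tests on baseline to week 12 change in VEP gamma, where "we have 80% power to detect moderate to large effects": d=.77 within a group and d=.53 across groups (Power Analysis). EEG sessions per child: 4 visits × 2 phases = 8. VEP recording success: more than 70% of PMS patients seen at the centre (Potential pitfalls). Intolerance rate: not given, so assumed below.

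**1. The plan's own figure.** Power = P(T > t(0.975, n−1)), with T noncentral t on n−1 degrees of freedom and noncentrality d√n.
- n=30, d=.53: noncentrality .53 × 5.477 = 2.90; power 80.1%.
- n=15, d=.77: noncentrality .77 × 3.873 = 2.98; power 79.2%.

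Both stated figures reproduce, on the assumption that every child supplies both phases.

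**2. Lost SAND pairs.** The plan states no power for the SAND. As an illustration only, give the SAND the same d=.53 and remove pairs:

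| Assumed loss | Pairs left | Power at d=.53 | d detectable at 80% |
|---|---|---|---|
| 0% | 30 | 80.1% | 0.53 |
| 10% | 27 | 75.5% | 0.56 |
| 20% | 24 | 70.1% | 0.60 |
| 30% | 21 | 63.7% | 0.64 |

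The 30% row takes the complement of the 70% success rate and applies it to all 30 children. Applied to the PMS group only, the loss is 0.30 × 15 = 4.5, leaving 25 or 26 pairs and power of 72.0% or 73.8%.

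**3. Repeated exposure.** If each session independently carries an assumed intolerance probability q, the chance of withdrawal before the eighth session is 1 − (1−q)^7: about 7% at q=1%, 13% at 2% and 30% at 5%. The chance of withdrawal at one of the four phase 1 sessions is 1 − (1−q)^4: about 4%, 8% and 19%.

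**4. The two-patient halt.** If an EEG withdrawal counted, and each of 30 children had an assumed probability p of it, P(at least 2) = 1 − (1−p)^30 − 30p(1−p)^29: 12% at p=2%, 45% at 5% and 82% at 10%.

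**5. The sections side by side.** Risks to the Subjects makes intolerable EEG a withdrawal. Potential pitfalls makes failed EEG a data loss. The individual stopping list does not name it, although the clause on the investigator's judgement could be used. The follow-up text neither names nor excludes the SAND.

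**The case against.** Several points on the other side stand.

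- The two EEG sentences can be read as graded: discomfort lets the family stop the recording, while intolerable discomfort leads to withdrawal. Expected EEG loss can coexist with some withdrawals, and analysing withdrawn children can be done with data already collected. A reader might infer that the sections cannot all be followed. They are unclear and incomplete, but not wholly incompatible.
- SAND scores obtained before withdrawal remain usable in a mixed model with subject random intercepts. A child who stops in phase 2 keeps all of phase 1 and some of phase 2.
- The 70% figure concerns PMS patients at the centre and counts failure for any reason. Trial children are selected on a pre-treatment VEP, so many who cannot tolerate the EEG would not be enrolled. The short stimulus, desensitization and mock sessions should lower the rate further.
- The rule does not by itself reduce power for VEP gamma at an untolerated session, because that recording is missing with or without it.

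A reader might also infer that the rule removes children according to sensory reactivity, and treatment responders most of all. The SAND does score tactile reactivity, and desensitization is planned, so a link is plausible. But the documents give no data on who fails the EEG. The primary subscale is hyporeactivity, whereas intolerance might relate more to hyperreactivity. The enrolled iASD children are chosen for a PMS-like VEP, so typical iASD hyperreactivity cannot be assumed for them.

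The sentence also protects children whom the protocol describes as unable to assent. Nothing here argues against that protection.

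**Conclusion.** The point holds as an unreconciled rule with an avoidable cost. Followed literally, it truncates the SAND and the other clinical outcomes for a reason unrelated to whether they can be measured, and it loses the within-child contrast for any child withdrawn in phase 1.

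The size is uncertain. Under assumed losses of 10% to 30% of pairs, illustrative SAND power falls from 80.1% to between 75.5% and 63.7%, and the lower end is an upper bound on the harm rather than an expectation. This assumes that the SAND has the d=.53 used for VEP gamma and that lost pairs contribute nothing.

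It would be tempting to conclude that separating EEG failure from withdrawal keeps the SAND at 30 pairs. The documents do not support that: it presupposes that the child continues crossover treatment and that nobody else drops out. Bias related to sensory reactivity remains possible, with unknown direction.

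**What to change.** Reconcile Risks to the Subjects, Potential pitfalls and both Stopping Conditions sections on three questions: whether an untolerated EEG means leaving the study, whether clinical outcome collection then continues, and whether such a withdrawal counts toward the two-patient halt.

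As a data-collection rule:
- Code an untolerated EEG as missing EEG, with its reason.
- Request the SAND and the other clinical scales at their scheduled visits from children who stop the EEG or are withdrawn in either phase, with family agreement, and name the SAND in the follow-up text.
- Report EEG non-tolerance by phase and by group, so that any selective pattern can be seen.

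Whether study treatment continues for such a child is for the sponsor and DSMB to state. The cost is a short amendment and some extra clinical visits. Some children will contribute a SAND without a VEP, so the analyses relating VEP to SAND will include fewer children than the SAND analysis.

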of iASD with constrained heterogeneity based on a biological marker. Fourth, given our strong preliminary data in PMS and iASD and existing infrastructure and pipeline for conducting clinical trials, we will test the feasibility and robustness of electrophysiological markers in the context of treatment with rhGH, a step which has yet to be taken successfully in the ASD literature. Fifth, we expect to predict a subset of iASD with high potential to respond to treatment with rhGH based on biological profiles related to PMS, making progress toward a more personalized medicine approach for ASD.

Approach

Aim 3: Evaluate the feasibility of electrophysiological markers as a measure of treatment response.

Introduction. The objective of this aim is to administer rhGH to participants with PMS and iASD to evaluate the feasibility of select electrophysiological biomarkers to: 1) detect change in neural response (engagement) and 2) predict treatment responders on clinical assessments (efficacy). We will also explore the relationship between rhGH dose, IGF-1 level, and electrophysiological response. Participants will be selected based on electrophysiological profiles with reduced $P_{60}-N_{75}$ VEP amplitudes, reflecting impaired glutamatergic function. **Approach:** We will employ a randomized, placebo-controlled, double-blind, crossover design with a four-week wash-out period between phases. **Rationale:** Successful completion of this aim will establish feasibility of select biomarkers for detecting treatment response and advance knowledge about developing targeted treatments for PMS and related subsets of iASD with impaired glutamatergic activity. We expect, based on preliminary data, that the knowledge gained will provide evidence of targeted brain engagement with rhGH, a mechanistic pathway, and evidence of clinical efficacy.

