For each AE the subject experiences, the subject's parents/guardians will be asked if they received medical attention defined as hospitalization, an emergency room visit or a visit to or from medical personnel (medical doctor/doctor of osteopathy or nurse practitioner) for any reason. This information will be recorded in the CRF.

Lack of Efficacy

Lack of efficacy per se will not be reported as an AE. The signs and symptoms or clinical sequelae resulting from lack of efficacy will be reported if they fulfill the AE or SAE definition.

Time Period, Frequency, and Method of Detecting AEs

All AEs occurring from the initiation of therapy until completion will be recorded on the Adverse Event form in the subject's CRF, irrespective of severity or whether or not they are considered medication-related. Onset of chronic illness (e.g. autoimmune disorders, asthma, type 1 diabetes and allergies) and conditions prompting emergency room (ER) visits or physician office visits that are not related to well-child care, injury, or common acute illnesses (e.g., upper respiratory tract infection, otitis media, pharyngitis, and gastroenteritis) will be reported during the entire study period. The investigator will inquire about the occurrence of AEs at every visit/contact during the study as appropriate. All AEs either observed by the investigator or a clinical collaborator or reported by the subject's parent/guardian spontaneously or in response to a direct question will be evaluated by the investigator. AEs not previously documented in the study will be recorded in the Adverse Event form within the subject's CRF. The nature of each event, date and time (where appropriate) of onset, outcome, intensity and relationship to drug administration should be established. Details of any corrective treatment should be recorded on the appropriate page of the CRF.

When an AE/SAE occurs, it will be the responsibility of the investigator to review all documentation (e.g., hospital progress notes, laboratory, and diagnostic reports) relative to the event. The investigator will then record all relevant information regarding an AE/SAE on the CRF or SAE Report Form as applicable. The investigator will attempt to establish a diagnosis of the event based on signs, symptoms, and/or other clinical information.

Follow-up of Adverse Events and Serious Adverse Events and Assessment of Outcome:

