After the initial AE/SAE report, the investigator will actively follow each subject and provide further information on the subject's condition. All AEs and SAEs documented at a previous visit/contact and designated as not recovered/not resolved or recovering/resolving will be reviewed at subsequent visits/contacts. Investigators will follow-up subjects with SAEs or subjects withdrawn from the study as a result of an AE, until the event has resolved, subsided, stabilized, disappeared, the event is otherwise explained, or the subject is lost to follow-up. In the case of other non-serious AEs, until they complete the study or they are lost to follow-up. Clinically significant laboratory abnormalities will be followed until they have returned to normal, or a satisfactory explanation has been provided. The investigator may perform or arrange for the conduct of supplemental measurements and/or evaluations to elucidate as fully as possible the nature and/or causality of the AE or SAE.

Regulatory Reporting Requirements for Serious Adverse Events:

All safety data will be reported to Safety Monitoring Board and IRB every six months, or, in the case of any major safety concern or question, immediately. If any study stopping condition occurs, this will be reported immediately, and the study will be halted, pending review by these agencies. The investigator has a legal responsibility to promptly notify, as appropriate, both the local regulatory authority and other regulatory agencies about the safety of a product under clinical investigation. Prompt notification of SAEs by the investigator to the Study Contact for Reporting SAEs is essential so that legal obligations and ethical responsibilities towards safety of other subjects are met. The investigator, or responsible person according to local requirements, will comply with the applicable local regulatory requirements related to the reporting of SAEs to regulatory authorities and the IRB. The protocol will be filed under Investigational New Drug (IND) exemption status with the US FDA.

Safety Measures

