Participants will undergo comprehensive medical evaluation by the study physicians. Medical history, family history, physical and neurological examination (including anthropometric measurements and fundoscopic exams), routine hematology, thyroid function, and blood chemistry (including liver profile), bone X-ray for bone age, and electrocardiography will be performed to determine eligibility for participation. Patients will be monitored for safety and tolerability at weeks 2, 4, 8, and 12 in both treatment phases – see Table 1 and 2. There are a number of tertiary outcomes designed to monitor the safety of rhGH (see Tables 1 and 2) and will be reported to the DSMB (see Stopping Conditions).

Our preliminary phenotyping studies characterizing cognitive and adaptive functioning in Phelan-McDermid syndrome suggest that these children and adults have ID. This sample was significantly delayed in receptive language, expressive language, and overall functional communication skills. We will specifically be recruiting children with iASD who also have ID. As such, it is impossible to directly query these children using verbal methods with respect to safety and tolerability. Instead, we rely on parent report using open-ended methods and a modified SMURF, in addition to physical and neurological exams, and laboratory measures.

Monitoring for AEs will be conducted during scheduled and unscheduled visits per clinical and laboratory assessments. If a subject develops significant neurological signs and symptoms (e.g. cerebrovascular event), they will be seen immediately for a comprehensive evaluation, appropriate treatment, and removal from active participation in the study. We will also apply criteria for attribution of AEs by means of the following descriptors and codes.

- unrelated to treatment 1
- unlikely related to treatment 2
- possibly related to treatment 3
- probably related to treatment 4
- definitely related to treatment 5

Stopping Conditions for Individual Subjects

The following criteria will be used to identify possible adverse treatment events, which will indicate the need to halt active participation of the subject in the rhGH study

- Withdrawal of Consent
- PI or any regulatory authority (Safety Monitoring Board, IRB) believe withdrawal is necessary for the subject's health, well-being, or best interests.
- PI or any regulatory authority believe that withdrawal is necessary for the subject's health, well-being, or best interests

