All safety data will be reported to the DSMB every six months and to the IRB annually, or, in the case of any major safety concern or question, immediately. If any study stopping condition occurs, this will be reported immediately and the study halted, pending review by the DSMB and IRB, and until the decision by regulatory authorities to resume, suspend or close the study has been made.

*Operationally, "halting" will ordinarily mean that no further screening of new subjects and no treatment initiation will occur until the safety issue has been investigated and resolved (i.e., a final decision has been made to resume, suspend or close the study has been made). Enrolled study participants who have no new symptoms or adverse effects will ordinarily be allowed to continue study observation or treatment without interruption while the safety issue is being investigated, unless it is the contemporaneous judgment of the PI or subsequent judgment of the Safety Monitoring Board or IRB that it is unsafe to do so, in which case all observation or treatment interventions will be suspended forthwith.

Tables

Table 1. Safety and Screening Measures

Measures*	Baseline	Week 4	Week 8	Week 12
Physical and neurological exam	X			X
Fundoscopy	X			X
Electrocardiography	X			X
Bone X-ray for bone age	X			X
Pregnancy Test	X			X
Height	X			X
Weight	X			X
Head circumference	X			X
Side effect monitoring**	X	X	X	X

*Safety measures will be performed at these time points in *both* phases of the crossover trial.

**In addition to the above, side effect monitoring will occur at week 2 by phone, or at any point in person as needed, in both phases.

Table 2. Laboratory Safety Measures

Measures	Baseline*	Week 4*	Week 8*	Week 12*
Electrolytes (Na, K, Cl, CO2)	X			X
Complete blood count	X			X
Liver function panel	X			X
Thyroid function (TSH/T3/T4)	X			X
Renal function (BUN/CR)	X			X
Hemoglobin A1c	X			X
Albumin	X			X
Glucose (fasting)	X			X
Insulin (fasting)	X			X
Lipid profile	X			X
IGF-1 / IGF-BP3	X	X	X	X

*Laboratory safety measures will be performed at these time points in *both* phases of the crossover trial

Table 3. Dose Titration Schedule

Week	Dose
Week 1 and 2	0.15 mg/kg/week divided into daily doses
Week 3 to 12	0.30 mg/kg/week divided into daily doses

Literature Cited

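### Children who receive rhGH in the second phase have no scheduled adverse event ascertainment after their last dose; those who receive it first have 16 weeks

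*Combined protocol and SAP*

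**What the plan says.** The design is a "crossover design with a four-week wash-out period between phases", and "each subject is randomized to one of two treatment sequences" (Data Analysis). Research Design sets each phase at 12 weeks. Table 3 has dosing continue to the end of the phase: "Week 3 to 12 0.30 mg/kg/week divided into daily doses".

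Safety Measures sets the contacts: "Patients will be monitored for safety and tolerability at weeks 2, 4, 8, and 12 in both treatment phases". The notes to Tables 1 and 2 of the safety section apply the same columns (baseline, weeks 4, 8 and 12) to each phase; for Table 1, "Safety measures will be performed at these time points in *both* phases of the crossover trial". Week 2 is a phone contact. Neither table has a column after week 12.

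The section on the time period for detecting AEs gives the recording window: "All AEs occurring from the initiation of therapy until completion will be recorded on the Adverse Event form in the subject's CRF". It does not say what is completed. The section on follow-up of AEs sets no time limit for serious events, AE withdrawals and clinically significant laboratory abnormalities; these are followed until they resolve, are explained or (for the first two) the child is lost to follow-up. For the rest the rule is shorter: "In the case of other non-serious AEs, until they complete the study or they are lost to follow-up".

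**The concern.** In a two-sequence crossover, the washout and second phase provide off-drug observation only for children who had active drug first. Unless the plan adds a closing contact, the other sequence has none. Safety ascertainment then depends on the order to which a child was randomised.

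This matters more here because Safety Measures says the children cannot be questioned verbally about tolerability. Detection rests on parent report, the SMURF interview, examinations and laboratory tests, so when contacts stop, active detection stops. Week 12 is also the only on-treatment time in each phase for fundoscopy, electrocardiography, bone X-ray and ten of the eleven laboratory rows. For children on rhGH second, those results arrive as the recording window closes. A non-serious, non-laboratory finding at that visit has no required follow-up.

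The plan also has no rule for assigning an event that starts in the washout to one treatment or the other.

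**Working it through.** The plan states no length of safety follow-up after rhGH, so there is no figure to reproduce. The check is schedule arithmetic.

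**Inputs**
- Phase length: 12 weeks (Research Design).
- Washout: 4 weeks, between phases only (Aim 3, Introduction).
- Contacts: baseline and weeks 2, 4, 8 and 12 of each phase (Safety Measures; Tables 1 and 2).
- Dosing through week 12 (Table 3).

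**Calendar for one child**
- Phase 1 is weeks 0 to 12, washout weeks 12 to 16, and phase 2 weeks 16 to 28 (12 + 4 + 12 = 28).
- Contacts fall at weeks 0, 2, 4, 8 and 12, then at 16, 18, 20, 24 and 28.

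**Scheduled off-drug observation = last scheduled contact − end of rhGH dosing**

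| Sequence | rhGH ends | Last contact | Weeks off drug | Contacts after rhGH (weeks since rhGH ended) |
|---|---|---|---|---|
| rhGH first | week 12 | week 28 | 28 − 12 = 16 | 5 (at 4, 6, 8, 12, 16) |
| rhGH second | week 28 | week 28 | 28 − 28 = 0 | 0 |

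The first off-drug contact in the rhGH-first sequence is the phase 2 baseline, where every row of Tables 1 and 2 is marked. No contact is listed inside the washout itself.

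**Does the meaning of completion matter?** Whether it means completing both blinded treatment phases or completing the study, the end point for a child who finishes is week 28. The contrast stays 16 versus 0.

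**Children affected.** The documents give no sequence ratio. At 1:1, 15 of 30 receive rhGH second. If the split lay anywhere between 12:18 and 18:12, also an assumption, the number would be 12 to 18 (40% to 60%). This is a share of children, not of events.

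**What still operates after week 28**

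| Situation | Covered? | Where |
|---|---|---|
| Serious AE, or withdrawal because of an AE | Yes, to resolution or stabilisation | Follow-up of AEs and SAEs |
| Clinically significant laboratory abnormality | Yes, until normal or explained | Follow-up of AEs and SAEs |
| Sign a parent perceives as serious | Only if the parent makes contact | Adverse Events Reporting |
| New AE starting after the last dose | No scheduled contact; outside the recording window | Time Period section |
| Non-serious, non-laboratory AE open at the final visit | Required follow-up ends at completion | Follow-up of AEs and SAEs |

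The last two rows are the gap.

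**The case against.** Three stronger readings are tempting, and the documents do not support them.

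**That rhGH-second children have no off-drug follow-up at all.** The event-driven rules above remain, unscheduled visits are provided for, and the investigator may arrange further evaluation of any AE. What is absent is scheduled follow-up and planned detection of new events.

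**That the named risks go unfollowed.** Risks to the Subjects lists intracranial hypertension and slipped femoral epiphysis. The definition of a serious AE includes a medical-judgment criterion that could cover either, and follow-up would then continue. The laboratory timing adds little, because significant laboratory abnormalities are already followed.

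**That the rhGH versus placebo AE difference is understated, or half of late events are lost.** Data Analysis specifies no AE comparison, and no section says that events are counted by phase of onset. Onset date and relationship to drug are recorded, with a five-level attribution code, so a washout event can be linked to rhGH. The window is defined by when an event occurs, so one that began on drug and was recognised later falls within its wording. The 50% figure is only the assumed share of children given rhGH second. The rate of post-dose events is not given and could be near zero.

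Two further objections hold in part. A phone call cannot re-examine a fundus or an electrocardiogram; it collects what parents see and the status of known events. Four weeks is the washout length, and no document ties it to the timing of late rhGH effects; its merit is that it matches the sequences. Also, the DSMB Charter was not among the documents and consent pages were removed, so a closing contact described only there cannot be ruled out.

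None of this removes the 16 versus 0 contrast in scheduled ascertainment.

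**Conclusion.** The concern holds for scheduled ascertainment. As written, safety observation after rhGH depends on sequence: 16 weeks and five contacts for rhGH first, none for rhGH second. The consequence is limited to new AEs starting after the last dose and non-serious, non-laboratory AEs open at the final visit. It applies to about half the children, assuming roughly 1:1 sequences and completion as scheduled. The effect on total AE incidence cannot be estimated from the documents, and bias in a treatment comparison is not shown. The change is worth making because it is cheap and improves safety capture in children who cannot report symptoms themselves.

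**What to change.** 1. In the section on the time period for detecting AEs, replace the undefined end point: record AEs from first dose until 4 weeks after the last dose of each phase, which is the existing washout length.
2. Collect the final window with one SMURF phone call per child 4 weeks after the end of phase 2, using the phone method already planned for week 2. The phase 2 baseline visit already closes the phase 1 window. Calling every child, whatever the sequence, keeps the blind.
3. Tabulate events with onset in the 4-week window under the phase just ended. Each treatment then has the same 4-week tail in both sequences.
4. In the section on follow-up of AEs, extend follow-up of non-serious AEs open at the last visit to that call.

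**Cost.** About 30 calls by existing staff and a short amendment. The last child's follow-up ends about 4 weeks later, at 28 + 4 = 32 weeks. Timeline allots months 21-27 to finish data collection: 7 months, or 7 × 52.18/12 ≈ 30.4 weeks if counted inclusively. For a child starting at the end of month 20 the overrun is about 32 − 30.4 = 1.6 weeks, for safety data only. Treatment and the efficacy analysis are unchanged.
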